3.7.2 Other Parameters

Baseline patient data will be included as concomitant study parameters. Relevant patient and clinical data including basic demographic information (age, gender, and ethnicity), known underlying diseases, previous antibiotic exposure within 90 days, and admission date will be extracted from the clinical database for correlation and risk factor analyses.

For patients diagnosed with CLABSI, information including the number of days a patient spent in the hospital prior to strain isolation, number of days and type(s) of antibiotics used in said patient, hospital-generated antibiograms for each strain, patient risk factors for nosocomial infection associated with an isolate, previous surgeries or hospitalizations of the patient prior to isolation, location of a patient within the hospital prior to strain isolation and ICU admission, and any other information pertinent to a specific strain that will not identify a patient will be collected.

3.8 Data Collection

3.8.1 Clinical and patient data collection

A form comprising all study parameters will be prepared for data recording and collection. The data will be collected and handled confidentially by the investigators.

3.9 Data Analysis

The data will be analysed using the SPSS Software. Descriptive statistics will be expressed as percentages unless otherwise stated. Categorical variables will be expressed as percentages and compared using the Chi-square or Fisher's exact test, whichever is appropriate. Variables with a univariate test value of less than 0.05 (p-value) will be included in a multivariate analysis using a logistic regression model. Odds ratios (OR) and 95% confidence intervals (CI) will be calculated to identify the risk factors associated with the development of CLABSI in patients. In all instances, a p-value of less than or equal to 0.05 will be considered significant.

FUNDING

This study will be funded by Teleflex Research Grant (RM50000).

RESEARCH DATA MANAGEMENT

All data collected will be handled confidentially according to the Good Clinical Practice Guidelines. The paper case report forms will be stored within a locked cabinet at the Department of Anaesthesiology, Faculty of Medicine, Universiti Malaya. The electronic case report forms will be kept in a password-protected laptop. Only the study investigators will have access to the research data. The data will be kept for seven years upon completion of study. The results of the study will be reported in a thesis. The results will also be presented in conferences and published in scientific journals.

POTENTIAL RESEARCH IMPACT

The usage of antimicrobial-impregnated central venous catheters (CVCs) among adult critically ill patient in the Intensive Care Unit (ICU) can reduce central line-associated bloodstream infections (CLABSIs) and this will translate to reduced patients' length of stay and healthcare costs.

GANTT CHART

	2023												2024											
Research Activities	3	4	5	6	7	8	9	10	11	12	1	2	3	4	5	6	7	8	9	10	11	12		
Ethics submission	█	█																						
Patient recruitment			█	█	█	█	█	█	█	█	█	█	█	█										
Data collection			█	█	█	█	█	█	█	█	█	█	█	█										
Data analysis															█	█	█							
Completion and submission of manuscript																		█	█	█				
Publication and scientific presentations																					█	█		

REFERENCES

- Alotaibi, N. H., Barri, A., & Elahi, M. A. (2020). Length of Stay in Patients With Central Line-Associated Bloodstream Infection at a Tertiary Hospital in the Kingdom of Saudi Arabia. *Cureus, 12*(10). <https://doi.org/10.7759/CUREUS.10820>

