2. OBJECTIVES

Primary objective:

- To compare the incidence of central line-associated bloodstream infection (CLABSI) rate in patients using antimicrobial-impregnated central venous catheter (CVCs) and non-impregnated CVCs in Malaysia adult Intensive Care Unit (ICU)

Secondary objectives:

- To determine the length of stay of patients using antimicrobial-impregnated central venous catheter (CVCs) vs non-impregnated CVCs in Malaysia adult Intensive Care Unit (ICU)
- To undertake a cost-effectiveness analysis in prevention of central line-associated bloodstream infection (CLABSI) between patients using antimicrobial-impregnated central venous catheters (CVCs) and non-impregnated CVCs in Malaysia adult Intensive Care Unit (ICU)
- To compare the antimicrobial resistance features of the bacterial species that caused central line-associated bloodstream infection (CLABSI) between patients using antimicrobial-impregnated central venous catheter (CVCs) and that of non-impregnated CVCs in Malaysia adult Intensive Care Unit (ICU)

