3.7.1.2 Secondary Outcomes

The secondary outcomes investigated included:

- i. ICU Length of stay of patients diagnosed with CLABSI
- ii. Healthcare costs of patients diagnosed with CLABSI
- iii. Antimicrobial resistance profiles of the bacterial species isolated from patients diagnosed with CLABSI

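### Section 3.9 names no continuous method for ICU stay or cost, and gives the baseline data already collected no role in comparing them between catheters

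*Combined protocol and SAP*

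**What the plan says.** Section 2 sets as a secondary objective "To determine the length of stay of patients using antimicrobial-impregnated central venous catheter (CVCs) vs non-impregnated CVCs", and lists a cost-effectiveness analysis as another. Section 3.7.1.2 defines the stay outcome more narrowly, as "ICU Length of stay of patients diagnosed with CLABSI", and restricts cost to the same patients.

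Section 3.9 is the whole analysis plan. It offers three tools:

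- a default summary: "Descriptive statistics will be expressed as percentages unless otherwise stated";
- between-group tests: "Categorical variables will be expressed as percentages and compared using the Chi-square or Fisher's exact test, whichever is appropriate";
- one model: variables with a univariate p-value below 0.05 "will be included in a multivariate analysis using a logistic regression model", whose purpose is "to identify the risk factors associated with the development of CLABSI in patients".

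Section 3.7.2 lists the baseline data: age, gender, ethnicity, "known underlying diseases, previous antibiotic exposure within 90 days, and admission date". It says that these "will be extracted from the clinical database for correlation and risk factor analyses".

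**The concern.** ICU days and cost are continuous and usually right-skewed. Section 3.9 gives no mean, median or measure of spread for them, and no test, model or effect estimate. Two secondary objectives therefore have no pre-specified analysis, and the summary, scale and covariates could all be chosen after the data are seen.

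The baseline data are a second, separate loss. If they predict stay or cost, adjusting for them sharpens the comparison between arms at no extra data-collection cost. As written they enter one place only, a model for CLABSI, and only after screening on p-values. Screening is a poor way to choose covariates for a treatment comparison: it depends on the observed data, and with few events it will often drop variables that matter for stay or cost.

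**Working it through.** **Plan's own figure.** The plan states no figure for stay or cost, so there is none to reproduce. Section 3.6 gives 50 patients, raised to 55 per arm for 10% dropout (50 × 1.1 = 55). I take 50 analysed per arm as given. Whether 50 suffices for the primary outcome is a separate question.

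**Inputs not in the documents (assumed).** Within-arm log-scale SD of stay 0.8; true ratio 1.5; three covariates; share of log-scale variance explained (R²) 0 to 0.3.

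**Step 1: unadjusted log-scale comparison.** The effect is ln(1.5)/0.8 = 0.405/0.8 = 0.507 SD. The noncentrality is 0.507 × √(50/2) = 2.534. With 98 degrees of freedom and two-sided 0.05, power is 71%. Simulation under the same assumptions gave 70–72%.

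**Step 2: adding three fixed covariates.** The residual SD falls by √(1 − R²). Three degrees of freedom are lost, and chance correlation with arm costs a factor of about √(95/98) = 0.985. The noncentrality becomes 2.534 × 0.985/√(1 − R²), with 95 degrees of freedom.

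| R² | Noncentrality | Power |
|---|---|---|
| 0 | 2.495 | 69% |
| 0.1 | 2.630 | 74% |
| 0.2 | 2.79 | 79% |
| 0.3 | 2.98 | 84% |

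A simulation of the adjusted regression gave the same values to within half a point.

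**Step 3: the same gain without assuming an SD.** At 80% power and 50 per arm, the detectable difference is 2.80 × √(2/50) = 0.56 SD. Multiplying by √(1 − R²) gives 0.53, 0.50 and 0.47 SD for R² of 0.1, 0.2 and 0.3. Equivalent unadjusted sizes, 50/(1 − R²), are 56, 63 and 71 per arm.

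**Step 4: the population in 3.7.1.2.** Expected CLABSI cases are 50 × catheter days × 0.01218 in the control arm, and 0.7 times that in the impregnated arm under the 30% reduction in 3.6 read as relative. Catheter days per patient are assumed. The detectable difference is 2.80 × √(1/m₀ + 1/m₁), where m₀ and m₁ are the two expected counts.

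| Days | Control | Impregnated | Detectable difference |
|---|---|---|---|
| 7 | 4.3 | 3.0 | 2.1 SD |
| 10 | 6.1 | 4.3 | 1.8 SD |
| 14 | 8.5 | 6.0 | 1.5 SD |

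With about 3 to 9 patients per arm, a model with three covariates plus arm is not workable.

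**Step 5: does a raw mean difference share the log-scale power?** Under the Step 1 assumptions, simulation gave:

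| Method | Power |
|---|---|
| Log-scale t-test | 70–72% |
| Mann-Whitney | 68–70% |
| Welch test on raw means | 57–58% |
| Percentile bootstrap of raw means | 62.5% (6.4% rejection under the null) |
| Median split, uncorrected chi-square | 58–59% |

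It does not. The case for a mean cost difference is that an economic comparison needs mean cost.

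**The case against.** The strongest reply is that the plan is merely silent. The chi-square and Fisher sentence is confined to categorical variables, and the percentage default is qualified. A reader might infer that stay and cost must be cut into categories, so that information is thrown away. No section says so, and that reading should not be pressed. The contrast of 58% power for a median split with 71% on the log scale describes an analysis nobody has proposed. Nor does it support analysing arithmetic means, which do about as badly as the split on power.

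A reader might also infer that the baseline data are reserved for CLABSI. Section 3.7.2 speaks of correlation and risk factor analyses, without limiting them to CLABSI or excluding other uses. The fair statement is that no use in the arm comparison is given.

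Next, an unadjusted comparison of randomised arms is valid. With 55 per arm, a factor present in half of patients differs by 10 percentage points or more between arms in 29% of trials (exact binomial 0.294). That is ordinary chance variation, already reflected in the unadjusted interval, and is not evidence of bias. This stands: adjustment buys precision, and only if the covariates are prognostic, which the documents do not show.

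Finally, the mismatch between sections 2 and 3.7.1.2 is the larger defect. That also stands, and it makes the adjustment conditional. But settling the population would still leave 3.9 without a method for either outcome.

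**Conclusion.** The point holds in a limited form. Section 3.9 names no continuous method for ICU stay or cost, its only covariate rule is p-value screening into a CLABSI model, and the baseline data have no stated part in comparing these outcomes between catheters. Asking only for a continuous summary would be a request for detail. The substantive gain is pre-specified adjustment for values already collected: about 3 to 13 points of power for stay at R² of 0.1 to 0.3, against a loss of one to two points at R² of 0.

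These figures rest on the assumed SD, ratio and R², and on 50 analysed patients per arm. They concern log-scale stay and should not be carried over to the cost difference. They do not apply to a CLABSI-only population. Because the outcomes are secondary and the unadjusted comparison is valid, this is a worthwhile improvement and not a threat to the trial's validity.

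**What to change.** 1. Reconcile sections 2 and 3.7.1.2 so that stay and cost are compared in all randomised patients. The rest depends on this.
2. In 3.9, limit the percentage sentence to categorical data.
3. Stay: linear regression of log ICU days on arm and the fixed covariates, reported as a ratio with 95% CI, with medians and interquartile ranges by arm. State how ICU deaths are handled.
4. Cost: adjusted difference in arithmetic mean cost between arms, with the same covariates and a bootstrap 95% CI.
5. Fix a small covariate set now, such as age, number of underlying diseases and antibiotic exposure in the previous 90 days, and keep it whatever the univariate p-values. The screened logistic model can remain as a separate exploratory analysis of CLABSI risk factors.

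Items 2 to 5 need only analysis-plan wording, and the covariates are already on the collection list. Item 1 also means recording stay and cost for every patient, if that is not already intended. The price is slightly more modelling and the small loss of power if the covariates prove uninformative.

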1.1 Research Questions

1. Is there any difference in central line-associated bloodstream infection (CLABSI) rates between patients using antimicrobial-impregnated central venous catheters (CVCs) and non-impregnated CVCs in Malaysia adult Intensive Care Unit (ICU)?

2. Does the use of antimicrobial-impregnated central venous catheters (CVCs) in central line-associated bloodstream infection (CLABSI) prevention in Malaysia adult Intensive Care Unit (ICU) affect patient length of stay when compared to non-impregnated CVCs?
3. Does the use of antimicrobial-impregnated central venous catheters (CVCs) in central line-associated bloodstream infection (CLABSI) prevention in the adult Intensive Care Unit (ICU) setting affect healthcare costs when compared to non-impregnated CVCs?
4. How antimicrobial resistance features of the bacteria causing central line-associated bloodstream infection (CLABSI) may differ in patients using antimicrobial-impregnated central venous catheters (CVCs) compared to non-impregnated CVCs?

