3.6 Sample Size

Our local data at ICU, UMMC reported the incidence of CLABSI per 1000 catheter days in the first 6 months of 2022, to be 12.18. Using SAS® for sample size calculation, in order to detect a clinically significant reduction of CLABSI by 30%, and assuming a two-sided type I error protection of 0.05 and a power of 0.80, we calculated a sample size of 50 patients is required. To incorporate a 10% drop out rate, we therefore aim to recruit 55 patients in each arm (antimicrobial-impregnated CVCs, n=55; non-impregnated CVCs, n=55). This will make up to a total sample size of 110.

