3.7 Variables/ Parameters

3.7.1 Dependent Variables

3.7.1.1 Primary Outcome

The primary outcome investigated is the central line-associated bloodstream infection (CLABSI) rate, expressed in cases per 1000 catheter days. The diagnosis of CLABSI will be based on the CDC-NHSN definition.

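### The primary outcome is a CLABSI rate per 1000 catheter days, but section 3.9 names only methods for the proportion of patients infected

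*Combined protocol and SAP*

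**What the plan says.** Four places in the combined protocol and SAP treat the primary question as one about a rate over catheter time:

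- Section 1.1, first research question: "Is there any difference in central line-associated bloodstream infection (CLABSI) rates between patients using" the two catheter types.
- Section 2, primary objective: "To compare the incidence of central line-associated bloodstream infection (CLABSI) rate in patients using" the two catheter types.
- Section 3.6, baseline for the sample size: "the incidence of CLABSI per 1000 catheter days in the first 6 months of 2022, to be 12.18".
- Section 3.7.1.1, primary outcome: "central line-associated bloodstream infection (CLABSI) rate, expressed in cases per 1000 catheter days".

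Section 3.9 is the only section on analysis. Its methods are:

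- For comparing groups: "Categorical variables will be expressed as percentages and compared using the Chi-square", with Fisher's test as the alternative where it suits the data better.
- For effect measures, which the section ties to risk factors and not to the arms: "Odds ratios (OR) and 95% confidence intervals (CI) will be calculated to identify the risk factors associated with the development of CLABSI in patients".
- For choosing what enters the model behind those estimates, a screen on single-variable results: "Variables with a univariate test value of less than 0.05 (p-value) will be included in a multivariate analysis using a logistic regression model".

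No rate ratio, rate difference, person-time test, Poisson-type model or time-to-event method appears anywhere, and section 3.9 does not say which analysis is primary.

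**The concern.** Each method in section 3.9 treats CLABSI as present or absent in a patient. The natural reading is that infected yes/no will be compared between arms by chi-square or Fisher's test. That comparison gives a patient with a 3-day catheter the same weight as one with a 20-day catheter, while a rate per 1000 catheter days does not. The only confidence interval named is for risk-factor odds ratios.

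The trial could therefore print a rate for each arm, but it has no planned test or interval for the difference between them. Either the reported p-value will belong to a different quantity from the stated outcome, or a rate method will be chosen after the data are seen. The two quantities nearly agree when catheter days are similar in the arms, and they separate when dwell differs.

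**Working it through.** Section 3.9 contains no figure to reproduce, so the check asks how far its quantity can depart from the stated outcome.

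**Inputs.** From section 3.6: control rate 12.18 per 1000 catheter days (0.01218 per day), a 30% reduction read as a rate ratio of 0.70, and 50 patients per arm before dropout. Assumed, because the documents do not give it: mean dwell of 7 to 14 days. The hazard is taken as constant.

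**1. Expected odds ratio.** With fixed dwell d, the proportion infected is q = 1 − exp(−rate × d). The odds ratio is [q_imp/(1 − q_imp)] / [q_ctl/(1 − q_ctl)]. For control at 10 days, q = 1 − exp(−0.1218) = 0.1147.

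| True rate ratio | Impregnated dwell (control 10 days) | q impregnated | Odds ratio |
|---|---|---|---|
| 0.70 | 10 | 0.0817 | 0.69 |
| 1 | 9 | 0.1038 | 0.89 |
| 1 | 8 | 0.0928 | 0.79 |
| 1 | 7 | 0.0817 | 0.69 |
| 0.70 | 12 | 0.0973 | 0.83 |
| 0.70 | 14 | 0.1125 | 0.98 |

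A dwell gap of 10 against 7 days with no effect on the rate gives the same odds ratio as a true 30% reduction at equal dwell. A gap of 10 against 14 days hides that reduction.

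**2. How often the tests reject.** Simulation with 50 per arm and 20,000 runs. Dwell is 2 days plus an exponential time, exposure stops at the first event, and significance is p ≤ 0.05. The section 3.9 rule is read as Fisher's test if any expected count is below 5, and uncorrected chi-square otherwise.

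| True rate ratio | Mean dwell, control vs impregnated | Section 3.9 rule | Exact rate test |
|---|---|---|---|
| 1 | 10 vs 10 | 4.3% | 2.3% |
| 1 | 10 vs 7 | 6.0% | 2.0% |
| 0.70 | 10 vs 10 | 6.1% | 3.9% |
| 0.70 | 10 vs 14 | 4.3% | 4.9% |

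**3. How large a dwell gap chance can give.** With equal rates and equal 10-day mean dwell, the central 95% range of the ratio of catheter days between arms is 0.73 to 1.38. Ratios of 7/10 = 0.70 and 14/10 = 1.40 lie just outside it.

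**4. A worked result.** Suppose 4 of 50 (impregnated) and 6 of 50 (control) are infected. The odds ratio is (4 × 44)/(46 × 6) = 0.64, Fisher p = 0.74, whatever the catheter days. For the rate ratio, the Clopper-Pearson limits for the impregnated share of events, 4 of 10, are 0.1216 and 0.7376. Each limit π converts to π/(1 − π) × (control days / impregnated days).

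| Catheter days, impregnated / control | Rate ratio | Exact 95% CI |
|---|---|---|
| 500 / 500 | (4/500)/(6/500) = 0.67 | 0.14 to 2.81 |
| 450 / 500 | (4/450)/(6/500) = 0.74 | 0.15 to 3.12 |
| 400 / 500 | (4/400)/(6/500) = 0.83 | 0.17 to 3.51 |

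The estimate moves with catheter days. The conclusion does not, because every interval is wide and includes 1.

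**The case against.** The strongest reply is that section 3.9 never says CLABSI will be compared between arms by chi-square or Fisher's test. Its sentence is a general rule for categorical variables, a rate is not a categorical variable, and the logistic model is tied to risk factors. The section also allows exceptions to percentages, so reporting rates by arm can be taken as planned. That reading is fair, but it leaves the primary outcome with no planned arm comparison at all, which is no smaller a gap.

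The second reply is that the practical effect is small, and much of this stands:

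- No passage shows that dwell will differ between randomised arms, and the most striking scenarios need a systematic difference.
- The contrast of 6.0% against 2.0% is not all due to the wrong quantity. At equal rates and equal dwell the figures are already 4.3% and 2.3%, so about half of the 4-point gap is the conservatism of the exact test.
- With about 7 to 13 events expected in total (rate ratio 0.70, 7 to 14 days' mean dwell), neither method has useful power.

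Third, the protocol requires a rate comparison but not this particular exact test. Poisson or negative binomial regression with log catheter days as offset would also match the outcome. That is so; the exact version is preferred because so few events are expected.

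**Conclusion.** The concern holds. The stated outcome is a person-time rate, and every inferential method named is a per-patient yes/no method that ignores catheter days. This follows from the text and does not depend on any dwell assumption.

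The size does depend on dwell. At equal dwell the odds ratio is 0.69 against a rate ratio of 0.70. At assumed dwell of 10 against 7 to 14 days, the odds ratio runs from 0.69 with no rate effect to 0.98 with a true ratio of 0.70. The simulated differences in rejection are about 1 to 4 percentage points, partly from test conservatism. The point must be fixed because the primary outcome has no pre-specified analysis, not because a large error rate has been shown. With so few events, the estimate and its interval will be the main result, and neither is planned.

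**What to change.** In section 3.9:

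- Name the primary analysis as the CLABSI incidence rate ratio, impregnated against non-impregnated. Test the impregnated arm's events as a binomial count against its share of catheter days, doubling the smaller tail for the p-value. Convert the Clopper-Pearson limits of that share to a ratio for the 95% CI, so that test and interval agree.
- Report events, catheter days and the rate per 1000 for each arm.
- Keep Fisher's test on patient proportions as supportive.
- State that the arm comparison does not depend on the univariate p < 0.05 screen.
- State how events and days are counted, for example the first CLABSI only, with days to first CLABSI or catheter removal. The documents do not dictate this choice, and it may differ from how the 12.18 benchmark was counted.

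Also confirm that the data form in section 3.8.1 records insertion and removal dates. Section 3.7.2 does not list them, although the form may already cover them as part of the primary outcome.

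The cost is a rewrite of one section and a check of the form. There are four drawbacks:

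- The rate analysis assumes a constant hazard.
- The exact test is conservative: 3.9% rejection against 6.1% for the section 3.9 rule at rate ratio 0.70 and equal 10-day dwell.
- The counting rule matters. With first events only, counting all days to removal would lower a true 12.18 to about 11.4, 11.1 or 10.6 per 1000 at 7, 10 or 14 days' mean dwell.
- The change does not cure the small number of expected events, or any selection from the exclusions in section 3.4 that can only be applied after insertion. Both need separate attention.

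### With about 8 CLABSIs expected, ordinary logistic regression in 3.9 can return infinite odds ratios, and the open choice between chi-square and Fisher can decide a sparse comparison

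*Combined protocol and SAP*

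**What the plan says.** Section 3.9 (Data Analysis) compares categorical variables by chi-square or Fisher's "exact test, whichever is appropriate". It gives no rule for choosing between them. Variables with a univariate p-value below 0.05 then enter a logistic regression, and "Odds ratios (OR) and 95% confidence intervals (CI) will be calculated to identify the risk factors associated with the development of CLABSI in patients". No estimation method or interval type is named, and SPSS is the stated software, so ordinary maximum likelihood with Wald intervals is the natural reading.

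Section 3.6 (Sample Size) supplies the inputs that determine how many events there will be. Local data "reported the incidence of CLABSI per 1000 catheter days in the first 6 months of 2022, to be 12.18". A 30% reduction is to be detected, "assuming a two-sided type I error protection of 0.05 and a power of 0.80". The result is that "we calculated a sample size of 50 patients is required", raised to 55 per arm for 10% dropout. Mean catheter days per patient and expected CLABSI counts are not given. Section 3.7.1.1 defines the primary outcome as a "rate, expressed in cases per 1000 catheter days". Section 3.7.2 lists candidate factors: age, gender, ethnicity, underlying diseases and antibiotic exposure within 90 days.

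**The concern.** Both methods in 3.9 behave poorly when events are few.

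In a logistic model, if every CLABSI falls on one side of a factor, the maximum-likelihood odds ratio is infinite. Software then prints a very large number with a Wald interval that carries no information. The p<0.05 screen is no safeguard, because a factor that separates the events completely can pass it easily.

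In a two-group comparison at low counts, chi-square and Fisher can fall on opposite sides of 0.05. If the choice is left open, it can be made after the split is known. What is at stake is risk-factor output containing odds ratios that do not exist, and a significance statement that depends on an unstated choice.

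**Working it through.** **Inputs.** Rate 12.18 per 1000 catheter days, 30% reduction (read as relative, so 8.526), two-sided 0.05 and 50 analysable patients per arm, all from 3.6. Catheter days per patient are assumed: 8 as the base, 5 to 20 as the range.

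**The plan's own figure.** The dropout step reproduces: 50 × 1.1 = 55. The 50 does not. Catheter days per arm for two Poisson rates are (1.96 + 0.8416)² × (λ1 + λ2)/(λ1 − λ2)² = 7.849 × 0.020706/0.003654², or about 12,170. That is 243 days per patient at 50 per arm. Read as proportions (12.18% vs 8.526%), the requirement is 1,091 per arm. This is a separate problem, but it explains why events will be few.

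**Expected events**, using p = 1 − exp(−rate × days):

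- 8 days: control 50 × (1 − e^(−0.01218×8)) = 50 × 0.0928 = 4.64; impregnated 50 × (1 − e^(−0.008526×8)) = 50 × 0.0659 = 3.30; total 7.9.
- 14 days: 7.84 + 5.63 = 13.5.

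**Why a zero cell matters.** Suppose 8 of 50 exposed and 0 of 50 unexposed patients have a CLABSI. The odds ratio is (8 × 50)/(42 × 0), which is infinite, and the Wald standard error contains 1/0. Fisher's p for this table is 0.0058, so the factor passes the screen.

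**How often, without the screen.** The chance that no CLABSI falls among the exposed is about (1 − q)^events for prevalence q.

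- 8 events: 0.8^8 = 0.168 and 0.7^8 = 0.058. For at least one of four factors: 1 − (1 − 0.168)^4 = 0.52 and 1 − (1 − 0.058)^4 = 0.21.
- 14 events: 0.044 and 0.0068, giving 0.16 and 0.03.

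**How often, with the plan's screen.** Many zero cells that arise only because a factor is uncommon now drop out: 0 of 8 at 20% prevalence has probability 0.168, so it cannot reach p<0.05. In simulated trials with 4 to 10 candidate factors at assumed prevalences, a selected factor still had a zero cell in roughly 11-25% of trials with 8 events and 3-9% with 14.

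A hand check at 50% prevalence gives the order of magnitude:

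- An unrelated factor separates 8 events with probability 2 × 0.5^8 = 0.0078. Over ten such factors this is 1 − (1 − 0.0078)^10 = 0.075; over four it is 0.03.
- A factor with an assumed true odds ratio of 3 has 75% of events exposed, so 0.75^8 = 0.10. Two such factors give 1 − 0.9² = 0.19. With 14 events, 0.75^14 = 0.018 each.

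**Two-group comparison, 7 vs 1 at 50 per arm.** Chi-square (uncorrected) p = 0.027; Fisher 0.059; Boschloo 0.037.

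**Size under the usual rule** (Fisher if an expected count is below 5, otherwise chi-square), by full enumeration of two binomials with both arms at the control rate:

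| Catheter days (assumed) | Fisher always | Two-test rule |
|---|---|---|
| 5 | 1.0% | 1.4% |
| 8 | 1.7% | 3.6% |
| 10 | 2.0% | 4.7% |
| 14 | 2.5% | 5.4% |
| 20 | 2.9% | 5.1% |

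Boschloo's size is 3.2% at 8 days and 3.3% at 10.

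**Power, 50 per arm:**

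| Risks | Fisher | Two-test rule | Boschloo |
|---|---|---|---|
| 9.3% vs 2% | 15% | 17% | 26% |
| 15% vs 3% | 40% | 49% | 51% |
| 20% vs 5% | 51% | 64% | 58% |
| Planned 30% reduction, 8 days | 2.7% | 4.7% | 5.1% |

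At 10 days and the planned reduction, the two-test rule has 7.0% and Boschloo 5.8%.

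**The case against.** A reader might infer that the planned analysis runs at about 1.7% instead of 5%. The documents do not support that. The 1.7% belongs to Fisher's test used on every data set, at an assumed 8 catheter days. Section 3.9 also names chi-square, and under the usual rule the size at 8 days is 3.6%. Nor does a size below 5% breach the error limit in 3.6; it costs power.

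It is also fair to say that 3.9 assigns neither test to the primary outcome, which is a rate. The lack of a named rate analysis is a larger gap, and Boschloo's test does not fill it. Boschloo is not uniformly better than the two-test rule either: it is about level at 15% vs 3% and lower at 20% vs 5%. The unreproducible sample size is the greater defect, and no choice of test repairs it.

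On the logistic model, one can object that risk factors are secondary to the treatment comparison and that the prevalences are assumed. Both are true. The frequency of zero cells depends on how many factors are candidates, how common they are and whether they are truly associated; four unrelated factors give only about 3% in the hand check. What stands is that the screen does not remove the problem, and that separation is most likely for the strong factors the analysis is meant to find.

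**Conclusion.** The point holds for the logistic model. With about 8 CLABSIs, a screened factor has a zero cell in roughly 11-25% of simulated trials, falling to 3-9% with 14. These figures rest on assumed catheter days (8 and 14), 4 to 10 candidate factors and assumed prevalences.

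The choice of two-group test is secondary. Leaving it open lets a 7 vs 1 split be significant or not, and under a below-5 rule the size drifts from about 1.4% to 5.4% over 5 to 20 assumed days. The case for Boschloo is one pre-named test that never exceeds 5% and is always at least as powerful as Fisher's. Its gain over the two-test rule is confined to sparse counts.

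**What to change.** In 3.9, before any outcome data are seen:

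1. State that the risk-factor model is fitted by Firth's penalised likelihood, with profile-likelihood 95% CIs in place of Wald intervals. The cost is slight shrinkage of the odds ratios and a short script or add-on beside SPSS. Intervals will still be wide with so few events.
2. Replace the open choice of test with Boschloo's exact unconditional test for comparing percentages of patients between arms. The cost is a sentence of text, a short script, and some power relative to the two-test rule when events are more frequent (58% vs 64% at 20% vs 5%).

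Neither change affects patients, recruitment or data collection. The sample size and the analysis of the primary rate need their own corrections.
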